## 5. Study design

### 5.1 Design

Study design and hypotheses. This will be a pragmatic randomized controlled trial to test the effect of adding home pulse oximetry to patients being started on COVID Watch as part of their routine care. In this adaptation to COVID Watch, after being deemed safe for outpatient management and started on COVID Watch patients will be randomly selected to receive a pulse oximeter via overnight mail with educational materials (Appendix Fig 6).

Patients sent a pulse oximeter will be prompted twice daily to text their oxygen saturation level after walking in place for 1 minute. If the oxygen saturation decreases by 3 percentage points or more to a level below 95% or if it falls below an absolute level of 90%, the patient will receive an immediate call from the same on-call RNs for COVID Watch and undergo the same triage protocol. Hypotheses: Provision of pulse oximetry will lead to a higher number of Days Alive and Out of Hospital and Emergency Department (H2a), particularly among Black and Latino patients (H2b) compared to COVID Watch alone.

Choice of study design. The researchers have chosen a pragmatic randomized control trial because it is the most rigorous design for obtaining causal effects of providing pulse oximeters to a remote home monitoring program for COVID-19 in real world settings with diverse populations while accounting for time-varying trends, such as advances in treatment that occur during the study period.

## **5.2 Study duration**

The study is expected to take 18 months to conduct, an expedited time frame in order to make results available as quickly as possible in the midst of the COVID-19 pandemic: 2 months for planning and approvals; a minimum of 5 months for data collection to reach the target sample size; 3 months for analysis, and 8 months for dissemination of results.

## **5.3 Target population**

The study population will be COVID-19 patients participating in COVID Watch as part of routine care via (1) outpatient testing, (2) ED/Inpatient COVID-19 testing with subsequent ED discharge or (3) ED/Inpatient testing with subsequent hospital discharge. Patients will be excluded from the trial if they are: 1) less than 18 years of age; or 2) were already participating in an alternate monitoring program (e.g., home health care, inpatient rehab, specialized remote monitoring programs for a defined patient group such as those with pregnancy, cancer, or deemed high-risk upon ED discharge). Recruitment will begin as soon as possible (target October 1) and proceed to approximately March 1, 2021, in order to provide reports in Year 1 of this investigation and meet the enrollment quota based on the sample size calculations (see below) and current COVID Watch patient volume (currently ~60 patients per week as of August 21, 2020).

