COVID Watch was first implemented on March 24, 2020 and has enrolled 3,628 patients through May 21, 2020 of which 1,295 were COVID-19 positive. Understanding the effect of COVID Watch with and without pulse oximetry on Black and Latino patients is important because communities of color have had disproportionately higher rates of COVID-19 morbidity and mortality nationally, and locally in Pennsylvania, ranking 5th total deaths, and New Jersey, ranking 2nd. Symptom monitoring apps and programs are commercially available. However, COVID Watch is uniquely embedded into its host healthcare system, UPHS. Patients are enrolled using the electronic medical record (EMR), escalations are addressed by UPHS nurses, and they are referred to UPHS-based telemedicine, primary care, and social services when appropriate. COVID Watch is a scalable operational platform for monitoring patients with home pulse oximetry readings. Whether remote monitoring with or without pulse oximetry helps COVID-19 patients stay safe at home is an urgent, patient-centered question. Finally, with COVID-19 surges projected in late 2020, health systems will need to be prepared with evidence-based strategies for managing more COVID-19 patients at home.

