## **6. Subject recruitment**

Since this is an evaluation of a health system intervention, patients will not be recruited or enrolled individually but instead an analysis will be conducted based on interactions with the health system. Based on target sample size estimates below, the researchers are seeking to enroll at least 1078 patients.

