## E. Final Statistical Analysis Plan

The primary analysis will be an intention to treat analysis among randomized patients with confirmed COVID-19. The researchers seek to enroll at least 204 Black or Latino patients in each arm to achieve 90% power to detect a mean difference of 1 DOAH, assuming a type I error rate of 0.05. Given that Black and Latino patients comprise 61% of the COVID Watch sample, this indicates a target minimum sample size of at least 1078 patients with confirmed COVID-19.

As the primary analyses, the researchers will use an intention-to-treat approach. The researchers also performed a per protocol analysis including only those patients who actively participated on their allocated protocol (e.g., responded to at least one text-message check-in). For both analyses, the researchers compared mean DAOH between study groups using two-sample t-tests. Adjustment for covariates via regression was not deemed necessary as all sociodemographic and clinical characteristics were well balanced between arms. The researchers also compared continuous secondary outcomes including mean number of outpatient visits, emergency department encounters, and hospitalizations using t-tests. The researchers compared categorical secondary outcomes using Fisher's Exact test. A prespecified subgroup analysis was completed by comparing outcomes for Black and Hispanic patients to White patients. Exploratory subgroup analyses were conducted for age strata and enrollment context (inpatient, outpatient, and ED). All tests were two-sided and a p-value  $< 0.05$  was considered statistically significant in the primary analyses. In subgroup analyses, to account for multiple testing, Bonferroni corrected p-value cut-offs are provided for the results in the supplementary tables. All analyses were conducted using R statistical software version 3.6.0 (R Foundation for Statistical Computing, Vienna, Austria. URL <https://www.R-project.org/>).

[Below is from original SAP]

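### The accrual statement in section 5.3 was not updated when the target rose to 1078, and whether the window fits depends on an unresolved unit: confirmed or all randomised patients

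*Combined protocol and SAP*

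**What the plan says.** Final protocol, section 5.3: recruitment, with a target start of October 1, will "proceed to approximately March 1, 2021, in order to provide reports in Year 1 of this investigation and meet the enrollment quota", on the basis of the sample size calculation and the programme's volume, "currently ~60 patients per week as of August 21, 2020". Section 5.2 allows "a minimum of 5 months for data collection to reach the target sample size".

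The quota is worded in two ways. In the final SAP (part E), "this indicates a target minimum sample size of at least 1078 patients with confirmed COVID-19", derived from 204 Black or Latino patients per arm, 90% power, a one-day difference and a 61% Black or Latino share. In section 6 of the final protocol, "the researchers are seeking to enroll at least 1078 patients", with no mention of confirmation.

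The programme takes suspected as well as confirmed cases (section 5.5). The Background says it "has enrolled 3,628 patients through May 21, 2020 of which 1,295 were COVID-19 positive". The amendment summaries (parts C and F) date the increase in sample size to December 17, 2020. They attribute it to lower-than-expected positivity and a lower-than-expected SD in programme data through November 30, and give a figure for neither.

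**The concern.** Section 5.3 rests the quota on a count of everyone started on the programme, while the SAP states the quota in confirmed cases. The section was edited for the final protocol, since its eligibility wording differs from section 5.3 of the original protocol, but the dates and weekly rate are identical in both. In between, the target went up and positivity was reported as lower than expected. Either change, taken alone, makes the target harder to reach in the same window.

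At stake is what the trial delivers when recruitment stops. A reader cannot tell whether it stops at about March 1, at 1078 randomised patients or at 1078 confirmed patients. These three rules can yield very different numbers of Black or Latino patients, the group for whom the plan states its only power figure.

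**Working it through.** **The plan's own target.** The original SAP's figure reproduces: 2 × 259 / 0.61 = 849.2, hence 850. The same formula with the final inputs gives 2 × 204 / 0.61 = 668.9, hence 669, not 1078. Reaching 1078 needs a further divisor of 669/1078 = 0.62. An unstated positivity of about 62% would supply it, and 1078 would then count all randomised patients. Read literally, 1078 confirmed patients would give 1078 × 0.61 / 2 = 329 Black or Latino patients per arm and about 98% power, well beyond what the SAP asks for.

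**SD.** None is stated. Inverting n per arm = 2 × SD² × (1.960 + 1.282)² / difference², with n = 204 and a difference of 1 day, gives SD = 3.12 (3.11 with the t distribution). The SD is therefore an assumption taken from the plan's own 204, not an independent check on it.

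**Window.** October 1 to March 1 is 151 days, or 21.6 weeks. The documents do not state the date of first randomisation. Part C says the eligibility change of November 2 preceded it, so November 2 is the earliest start the log implies: 119 days, or 17.0 weeks.

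**Yield.** Starts = 60 × weeks. Confirmed = starts × 1,295/3,628 (0.357). Black or Latino per arm = confirmed × 0.61 / 2. Power is for a one-day difference, two-sided 0.05, with the back-solved SD.

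| | From Oct 1 | From Nov 2 |
|---|---|---|
| Starts | 1,294 | 1,020 |
| Confirmed | 462 | 364 |
| As share of 1078 | 43% | 34% |
| Black or Latino per arm (plan: 204) | 141 | 111 |
| Power, Black or Latino comparison | 77% | 67% |
| All confirmed, per arm | 231 | 182 |
| Power, all confirmed, same SD and effect | 93% | 86% |

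**What would be needed at 35.7%.** For 1078 confirmed: about 140 starts per week from October 1, 178 from November 2, or about 50 weeks at 60 per week. For 669 confirmed: about 87 or 110 per week, or about 31 weeks at 60.

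**Range over positivity (assumed values).** October 1 / November 2 starts:
- 25%: 324 / 255 confirmed; Black or Latino power 62% / 52%.
- 50%: 647 / 510 confirmed; power 89% / 81%.
- 62%: 802 / 632 confirmed; 245 / 193 Black or Latino per arm; power 94% / 88%.

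**The all-randomised reading.** If 1078 counts everyone randomised, the window gives 1,294 (quota met) or 1,020 (about 5% short). With 62% positivity, the per-arm Black or Latino count is likewise met from October 1 and about 5% short from November 2.

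**The case against.** The strongest reply is that 1078 is simply mislabelled in the SAP. Section 6 omits confirmation, the amendment cites positivity, and 669/0.62 lands on 1078. On that reading the window roughly works and the shortfall largely disappears. This is plausible, and it is why the size of the gap cannot be stated without first settling the unit. But the final SAP says confirmed, no document states 62%, and the only share that can be computed is far lower. One current section needs correcting either way.

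Second, the inputs come from different periods. The 35.7% is from March 24 to May 21, 2020, when starts averaged about 438 per week (3,628 over 8.3 weeks); the 60 per week is from August. At spring volume and spring positivity (about 156 confirmed per week), 1078 confirmed would take about 7 weeks. The Background also expects surges in late 2020. This stands as a limit on prediction. It does not rescue section 5.3, which bases its claim on the August rate and offers no other.

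Third, the end date is approximate, five months is a minimum and both targets are floors. Extension is therefore not excluded, and nothing commits the investigators to stop short.

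A reader might also infer that the trial as a whole has only 67 to 77% power. The documents do not support that. The figure belongs to the Black or Latino comparison at a back-solved SD. The primary analysis covers all confirmed randomised patients, for whom power would be about 86 to 93% at the same SD and effect.

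**Conclusion.** The accrual statement in section 5.3 is out of date and does not agree with the SAP's target as worded. At 60 starts per week and 35.7% positivity, the window yields about 364 to 462 confirmed patients, short of both 1078 and 669. It gives 111 to 141 Black or Latino patients per arm against 204, and about 67 to 77% power for that comparison where the plan states 90%.

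The result rests on a spring positivity, an August volume, an SD inferred from 204 per arm, and two start dates of which neither is documented as actual. October 1 precedes the October 8 approval; a start on that day gives about 441 confirmed and 75% power. If the baseline data through November 30 imply a start near December 1, the figures are about 275 and 55%.

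It does not follow that recruitment would fail. Volume could rise, the end date could move, and if 1078 means all randomised patients at about 62% positivity, the window roughly fits (1,020 to 1,294 randomised, 88 to 94% power). The firm conclusion is that sections 5.3 and 6 and the SAP cannot all stand as written.

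**What to change.** 1. State the target in one unit in section 5.3, section 6 and the SAP: either 669 confirmed patients, or 1078 randomised patients with the assumed positivity given. Show the derivation and the SD.
2. In section 5.3, replace the August 2020 rate with the current weekly volume and the positivity seen in the programme data already used for the December 17 amendment.
3. Either tie the end of recruitment to 204 confirmed Black or Latino patients per arm, the count that carries the stated power, or keep the March date and restate the expected confirmed count and power, separately for Black or Latino patients and for all confirmed patients.

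The cost is protocol and SAP wording. If the date is kept, the stated power may become less favourable; if the count is kept, recruitment may run past March 1.

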## **5.4 Accrual**

This is an evaluation of a health system intervention involving patients treated in 5 emergency departments and 530 affiliated outpatient practice sites at the University of Pennsylvania Health System that already places patients with suspected COVID-19 into a remote home monitoring program as part of usual care.

## **5.5 Key inclusion criteria**

The study population will be patients with suspected or confirmed COVID-19 started on COVID Watch as routine care via (1) outpatient COVID-19 testing or (2) ED/Inpatient COVID-19 testing with subsequent ED discharge or (3) ED/Inpatient testing with subsequent hospital discharge.

## **5.6 Key exclusion criteria**

Patients will be excluded if they are: 1) less than 18 years of age; or 2) were already participating in an alternate monitoring program (e.g., home health care, inpatient rehab, specialized remote monitoring programs for a defined patient group such as those with pregnancy, cancer, or deemed high-risk upon ED discharge)

## **6. Subject recruitment**

Since this is an evaluation of a health system intervention, patients will not be recruited or enrolled individually but instead an analysis will be conducted based on interactions with the health system. Based on target sample size estimates below, the researchers are seeking to enroll at least 1078 patients.

## **7. Subject compensation**

No compensation will be offered in this study.

## **8. Study procedures**

### **8.1 Consent**

This trial will be conducted under a waiver of the requirement for informed consent based on the following criteria set forth by the Federal Policy for the Protection of Human Subjects (the “Common Rule”):

1. The research involves no more than minimal risk to subjects.
2. The waiver will not adversely affect the rights and welfare of the subjects.
3. The research cannot be practicably conducted without a waiver of the requirement for informed consent.

**The research involves no more than minimal risk to subjects.** The risks to subjects of participating in this study is no more than minimal because both interventions exceed the standard of care routinely provided to patients diagnosed with COVID-19 managed at home. The current standard of care for patients with COVID-19 who are residing at home is to go to the ED for worsening symptoms. UPHS has implemented COVID Watch to enhance this standard of care by providing text-based assessments, two times a day for 14 days and escalates care to a nurse via telemedicine for any reported worsening of symptoms not severe enough to recommend going to the ED immediately. This service is provided free of charge to patients, a benefit to patients without insurance or established primary care. UPHS already offers a version of COVID Watch with pulse oximetry to patients with COVID-19 being discharged from the ED who meet specific criteria: a discharge pulse ox less than 95%, an infiltrate on chest x-ray, are or age of 60 years or older, or who are deemed by the ED clinician to have significant comorbid conditions. For this study, additional patients will be offered pulse oximetry, those eligible for COVID Watch but not meeting these additional criteria used in the ED. These individuals will be randomized to receive a pulse oximeter via overnight mail. Patients who prefer not to use the pulse oximeter will be free not to and continue on in COVID Watch. Those who use the pulse oximeter will still be escalated to a nursing assessment if they report a worsening of their respiratory symptoms even if they report a normal pulse oximetry reading. Furthermore, pulse oximetry devices are commercially widely available for patients to purchase, and patients may choose to use a pulse oximetry device irrespective of randomization for this study.

**The waiver will not adversely affect the rights and welfare of the subjects.** The intervention arm of this study (i.e., those randomized to receive a pulse oximetry) does not disrupt their eligibility or ability to receive care from the COVID Watch program. Therefore, the researchers do not anticipate the waiver will adversely affect the rights and welfare of subjects. Patients will retain the full right not to use the mailed pulse oximeter in addition to COVID Watch. A statement on the existing COVID Watch website will indicate that their data may be anonymized and used to study the impact of the program. The website will provide the contact information for a research coordinator if the patient wishes to not have their data to be analyzed for research purposes. The text message invitation to enroll in COVID Watch will include a link to this information. This statement will continue to be pushed to all patients placed into COVID Watch during the course of this trial.

**The research aims cannot be practicably conducted without a waiver of the requirement for informed consent.** This trial seeks to evaluate the effectiveness of adding home pulse oximetry to the existing, standard of care COVID Watch remote monitoring program in an overall population of patients with suspected or confirmed COVID-19. Requiring individual informed consent would introduce important selection biases. Specifically, socioeconomically disadvantaged populations who have experienced the greatest burden from COVID-19 have historically participated in research at lower levels than the general population and would be less likely to enroll in this study. A major goal of this study is to understand and create knowledge that is generalizable to these marginalized populations. Furthermore, unlike a drug trial where outcomes are primarily determined by physiologic effects of a medication, in this study of behavioral interventions, those who consent are likely to have behavioral characteristics that are not representative of those who would not consent and therefore potentially biasing the outcomes of a behavioral study. Therefore, requiring consent would render the study invalid since it would not have generalizability in applying to the desired population, particularly those experiencing the greatest disparities in outcomes due to COVID-19. Second, requiring informed consent would lead to delays in the distribution of pulse oximeters for a condition with an intense, but short disease course that could further reduce the generalizability of study results for health systems considering pulse oximeters for COVID-19 patients.

## 8.2 Procedures

1. Patients are started on COVID Watch as routine care based on confirmed or clinical suspicion for COVID-19 via the integration of the Way To Health (W2H) platform with the electronic health record.
2. Patient receives a text message to proceed in COVID Watch as is current routine care.
3. For this study, W2H auto-generates and sends the study's Research Coordinator (RC) a daily excel report with a list of new COVID Watch enrollees at regular intervals (e.g., every 2 hours). The report includes the randomized arm assignment (COVID Watch or COVID Watch + Pulse Oximetry), along with the patient's phone number.
4. The RC alerts patients randomized to COVID Watch + Pulse Oximetry via phone call and/or text message that there will be a next day pulse ox device delivery and that once received, the patient will start to measure and report their oxygen levels. The RC confirms the patient's mailing address and instructs patients that in the meantime, they should continue to respond to COVID Watch check-ins per standard protocol. The patient is instructed to text or call once they have received the pulse oximetry device. If language preference is Spanish, an interpreter is required on the call.

- i. If the patient cannot be reached by text, the RC calls and if necessary, leaves a voicemail and the patient will still be sent a pulse ox.
- 5. The RC sends a pulse oximetry device via UPS 11am and 5pm. The package will include a pulse oximetry device (with barcode), printed patient instructions in the appropriate language, and prepaid, labeled return envelope to be used at the end of their COVID Watch enrollment
- 6. The RC logs device identifier, date and time of drop off of package for each patient
- 7. The RC tracks device receipt (via both UPS tracking and/or patient self-report) and contacts the patient via text and/or phone call to ensure the patient understands how to use the device. If language preference is Spanish, an interpreter is required on the call.
- 8. The RC changes patient protocol from COVID Watch to COVID Watch + Pulse Oximetry.
- 9. The RC follows up with patients via text and/or phone call in the event that the device is not returned within 2 weeks of being discharged from COVID Watch

## 9. Human research protection

**COVID Watch patients.** The target population for the COVID Watch program will be any patient 18 or older evaluated and tested for suspected COVID-19 throughout any of the Penn Medicine access points, including the Emergency Department, calls to the hospital or outpatients centers, occupational health, and testing sites. Using established clinical resources as well as Penn OnDemand telehealth system, patients will be presented the option to enroll in the COVID-Watch program.

**COVID Watch** (<https://covidwatch.waytohealth.org/>) is an automated, text-based, remote monitoring program for patients infected with COVID-19 (i.e., laboratory confirmed). The intervention was designed by a team of clinical, technological, innovation, and analytic experts. Since hypoxemia is the primary driver of admission and fatality among COVID-19 patients, the researchers focused the algorithm on dyspnea, or shortness of breath, the closest approximation for concerning hypoxemia. Given the rapid and unpredictable decompensation of COVID-19 patients, patients receive clinical support 24 hours/day, 7 days/week. COVID Watch sends twice-daily, scheduled text messages to assess patients for shortness of breath using an algorithm to determine whether patients need an urgent escalation to a team of dedicated, on-call nurses within 1 hour. These nurses are supported by an on-call team of clinicians who can conduct urgent phone or video assessments. At each level patients' clinical needs are managed either via self-care advice, prescriptions, or referral to the ED. Patients are able to text the dedicated COVID Watch phone number and receive a response from clinical support within an hour.

**Pulse Oximeter.** The pulse oximeter device is used to monitor a patient's oxygen saturation levels in the body. The device is small and lightweight and is placed on the finger for measurement. As part of COVID Watch, patients are instructed on how to use the device and understand and report its readings. During enrollment into COVID Watch, the patient's baseline oxygen saturation level (SpO2) is collected and entered into Way to Health. During COVID Watch monitoring period the patient will collect SpO2 measurements. Patients with a decrease in SpO2 by 3 or more percentage points to a level below 95% or with a reading below an absolute value of 90% triggered a care escalation alert to COVID Watch telemedicine clinician team via Way to Health.

Pulse Oximeter data is automatically stored in Way to Heath and will be extracted from Way to Health platform in .csv format and stored on PMACs secure server.

